4.4.4 VISIT 3: FOLLOW UP & STUDY EXIT

Participants will attend the visit having not used any eye drops or eye makeup on the day of the visit.

- Monocular and binocular logMAR visual acuity will be recorded with high contrast letters under high illumination.
- Contact lens fit will be assessed.

Participants will be required to adapt to the room environment for at least 15 minutes prior to reporting subjective monocular ratings and performing evaporimetry measurements. The participant will apply thin layer of petroleum jelly will be applied to the skin surrounding the eye using a cotton tipped applicator to minimize the amount of evaporation from the skin.

- The participant will be asked to give subjective monocular ratings for:
 - Comfort
 - Dryness
 - Burning or stinging
- Evaporimetry measurements with contact lenses. Evaporimetry measurements will not be taken until the study lenses have been worn for a minimum of 6 hours.
- Non-invasive pre-lens tear film break up time (Tearscope)
- Lipid layer thickness (Tearscope)
- Lipid layer thickness (LipiView II)
- The participant will wipe away petroleum jelly from the skin surrounding the ocular surface using a tissue.
- Contact lens removal.
- Slit lamp biomicroscopy.
- Exit monocular and binocular logMAR visual acuity will be recorded with high contrast letters under high illumination with spectacles or spectacle refraction.

Study Exit

- The study exit form will be completed when a participant exits the study. This will occur either at study completion, or if the participant is discontinued from the study at another time. A study exit form must be completed for all participants who have been given a study number. If in the opinion of the investigator post-study follow-up visits are required, the exit form will be completed after the last follow-up visit.
- The participant will be discharged and will sign the study completion forms and receive remuneration for participating in the study.

4.4.5 UNSCHEDULED VISITS

An unscheduled visit is defined as an interim visit requested by the participant or investigator due to an unanticipated problem. Data recorded at these visits will be entered into the database. Only relevant and applicable unscheduled visit information will be included in the final report as deemed necessary by the lead investigator.

4.5 STUDY PROCEDURES

Table 3 summarizes the visits and procedures for the study.

Table 3: Summary of procedures to be conducted at scheduled visits

| Procedure | Visit 1 | Visit 2 | Visit 3 | Instrument/application |
|----------------------------------------------|---------|---------|---------|--------------------------------------|
| Informed consent (screening) | √ | | | Investigator |
| Demographics | √ | | | Investigator |
| Contact lens history | √ | | | Investigator |
| Medical history | √ | √ | √ | Investigator |
| CLDEQ-8 | √ | | | Questionnaire (paper) |
| VA with spectacles or refraction | √ | √ | √ | Visual acuity chart |
| Meibomian gland assessment | √ | | | Meibomian Gland Evaluator (overhead) |
| LD margin assessment | √ | | | Stamp |
| Stamp biomicroscopy (with staining) | √ | | √ | Stamp |
| Confirmation of inclusion/exclusion criteria | √ | | | Investigator |
| Training of study nurses | √ | | | Investigator |
| VA with contact lenses | √ | √ | √ | Visual acuity chart |

| Procedure | Visit 1 | Visit 2 | Visit 3 | Instrument/application |
|------------------------------------------------------------|---------|---------|---------|------------------------------------------|
| Over-refraction | √ | | | Phoropter |
| Lens fit assessment | √ | √ | √ | S t amp |
| Anterior eye photography | √ | | | S t amp and camera |
| Evaporimetry practice | √ | | | Evaporimeter |
| Removal of contact lenses | √ | | √ | Participant |
| Measurement of volume inside the goggle | √ | | | Modified swimming goggle |
| S t amp biomicroscopy (safety with staining) | √ | | | S t amp |
| S t amp biomicroscopy (white light) | | √ | | S t amp |
| Subjective assessment (comfort, dryness, burning/stinging) | | √ | √ | Questionnaire (paper) |
| Application of petroleum jelly | | √ | √ | Participant |
| Evaporimetry | | √ | √ | Prototype evaporimeter |
| Non-invasive breakup time | | √ | √ | Keeler Tearscope |
| Lp d layer thickness | | √ | √ | Keeler Tearscope, TearScience Lp View II |
| Removal of petroleum jelly | | √ | √ | Participant |
| Study completion and exit | | | √ | N/A |

4.5.1 DEMOGRAPHICS

Demographic information will be obtained from the participant, including age and sex.

4.5.2 CONTACT LENS HISTORY

Information will be obtained from the participant, including the type of contact lenses they currently wear, the solution that they use, and how often they wear their lenses.

4.5.3 MEDICAL HISTORY

At the screening visit, medical history questions to determine any current medications, allergies and relevant medical conditions will be asked and documented. At subsequent visits, participants will be asked about changes in their medication or medical condition(s).

4.5.4 CONTACT LENS DRY EYE QUESTIONNAIRE (CLDEQ-8)

The CLDEQ-8 is a dry eye questionnaire that asks the participant to reflect and rate their symptoms of eye discomfort and dryness over the past two weeks. A higher composite score indicates more severe dryness and the range is 0-37. A score of <12 will be considered asymptomatic and a score ≥ 12 will be symptomatic.

4.5.5 LOGMAR VISUAL ACUITY

Distance logMAR visual acuity will be measured using high contrast computer-generated acuity charts in high illumination room lighting. Participants will be asked to read letters, which progressively decrease in size on a computer screen at a viewing distance of 6 meters, with their habitual glasses/spectacle refraction or study contact lenses.

4.5.6 MEIBOMIAN GLAND ASSESSMENT

Participants will be seated at a slit lamp biomicroscope with the magnification set to 10x or 16x. The participant will be asked to look up and away from their nose. The meibomian glands will be manually expressed using the MG Evaluator (TearScience/J&J). The MG Evaluator will be depressed halfway to apply a pressure of 1.2 g/mm² to three separate areas (nasal, central, temporal) on the lower eyelid just below the lash line and angled down approximately 15 to 45 degrees. Five consecutive glands in each area will be assessed for expressibility as follows: 0: no secretion (including capped orifices), 1: inspissated (semi-solid, toothpaste like), 2: colored/cloudy liquid, 3: clear liquid oil. The results for each eye will be summed (Meibomian Gland Score).

4.5.7 LID MARGIN ASSESSMENT

The participant will be seated at a slit lamp biomicroscope.

Vascularity of the margin (erythema)

The vascularity of the lid margin will be graded (0-4 scale; 0: none, 1: minimal, 2: mild, 3: moderate, 4: severe).

Amount of lash loss

The amount of lash loss will be assessed (0-4 scale; 0: none, 1: minimal, 2: mild, 3: moderate, 4: severe).

Lid margin edema

The presence or absence of lid margin edema will be recorded.

Lid margin telangiectasia

Lid margin telangiectasia will be graded (0-4 scale, 0: none; 1: single telangiectasia; 2: 2 to 5 telangiectasia; 3: >5 telangiectasia; 4: severe-entire lid involvement).

Tear film debris

The presence or absence of tear film debris will be recorded.

4.5.8 SLIT LAMP BIOMICROSCOPY

A slit lamp biomicroscopy examination will be conducted to assess anterior segment ocular health. Ocular findings will be graded using the Efron grading scale (0-4, 0.5 steps – unless otherwise stated):

External adnexa anomalies

The presence or absence of external adnexa anomalies will be recorded. If adnexa anomalies are detected, the anomaly will be described.

Bulbar and limbal hyperemia

The redness of the bulbar and limbal conjunctiva of both eyes will be assessed using the Efron Grading scale (0 to 4, 0.5 steps).

Scars or other corneal observations

The presence or absence of scars or other corneal observations will be recorded. If scars or other corneal observations are detected, the finding(s) will be described.

Infiltrates

The presence or absence of infiltrates will be recorded. If present, the number and location will be recorded. The size (diameter in mm) and depth of the largest infiltrate (0-4 scale, 1 step) in the central, mid-periphery and periphery will be noted.

Endothelium abnormalities:

The presence or absence of endothelium abnormalities will be recorded. If endothelium abnormalities are detected, the finding(s) will be described.

Anterior chamber

The presence or absence of anterior chamber reaction will be recorded. If an anterior chamber reaction is detected, the finding(s) will be described.

Other abnormalities

The presence or absence of other abnormalities will be recorded. If other abnormalities are detected, the finding(s) will be described.

Corneal and conjunctival staining and indentation

A sodium fluorescein strip, wetted with a few drops of saline, will be applied to the superior bulbar conjunctiva of both eyes. Corneal staining type will be graded using the Efron scale (0 to 4, 0.5 steps), staining extent and depth will be graded on a (0 to 4 scale, 1 step) while viewing with cobalt blue light and Wratten filter (if available). Conjunctival staining and indentation will be graded using a 0 to 4 scale (0.5 steps), with larger values indicating increasing severity.

Mucin ball impressions

The number of mucin ball impressions will be recorded.

Palpebral conjunctival hyperemia and papillae (roughness)

The redness and roughness of the upper and lower eyelids will be assessed using the Efron scale (0 to 4, 0.5 steps).

4.5.9 CONTACT LENS FITTING

The acceptability of the fit of the study lenses will be assessed using a slit lamp biomicroscope after the lenses have settled for at least 10 minutes. Lens fit (centration, movement, limbal coverage, tightness/push up test, overall fit) will be determined to be either acceptable or unacceptable. Lens deposits will be recorded as present/absent. The participants will be asked to report if the lenses are subjectively comfortable (yes/no) at the screening visit.

4.5.10 ANTERIOR EYE PHOTOGRAPHS

The participant will be seated at a Zeiss slit lamp attached to a Canon EOS 60D digital camera. A photograph of each eye will be taken at 5x magnification with additional external illumination provided by a Canon Macro Twin Lite flash. The participant will hold a ruler underneath each eye while the photographs are taken. The ruler will serve as a calibration reference when the images are analysed with ImageJ in order to determine the size of the ocular surface in mm². The ruler will be cleaned with an alcohol wipe prior to being given to each participant.

4.5.11 MEASUREMENT OF VOLUME INSIDE THE GOGGLE

The participant will be seated in a consulting chair and will be asked to rest their head on the headrest. A pair of swimming goggles (Arena Zoom X-Fit), which are the same make and model as the prototype evaporimeter, will be used. The swimming goggle has been modified by drilling a small hole into the top of each lens. The participant will be asked to place the goggle over both eyes and to tighten the strap. A plastic, needleless syringe, with a 200 µl pipette tip attached to the end of the syringe, will be filled with saline (Bausch & Lomb Sensitive Eyes Saline Plus). Participants will be asked to keep their eyes closed while saline is added to the goggle. Saline will be added to each swimming goggle until the goggle has been filled with saline. The amount of saline added to each goggle will be recorded in milliliters. When the goggle is ready to be removed, the participant will be advised to tilt their head forward and continue to keep their eyes closed. A plastic tub will be placed below the participant's face and paper towels will be placed around the goggle to catch any saline that may spill out of the goggle. When the goggle has been removed, the participant will be advised to wipe their face with a paper towel while their eyes are kept closed. The swimming goggle will be cleaned with an alcohol wipe prior to use on each participant. A new sterile, syringe will be used for each participant. New saline and a new pipette tip be used to fill each goggle.

4.5.12 SLIT LAMP BIOMICROSCOPY (SAFETY VARIABLE)

The participant will be seated at a slit lamp at the following will be assessed in both eyes for:

External adnexa anomalies

The presence or absence of external adnexa anomalies will be recorded. If adnexa anomalies are detected, the anomaly will be described.

Bulbar and limbal hyperemia

The redness of the bulbar and limbal conjunctiva of both eyes will be assessed using the Efron Grading scale (0 to 4, 0.5 steps).

Scars or other corneal observations

The presence or absence of scars or other corneal observations will be recorded. If scars or other corneal observations are detected, the finding(s) will be described.

Infiltrates

The presence or absence of infiltrates will be recorded. If present, the number and location will be recorded. The size (diameter in mm) and depth of the largest infiltrate (0-4 scale, 1 step) in the central, mid-periphery and periphery will be noted.

Corneal and conjunctival staining and indentation

A sodium fluorescein strip, wetted with a few drops of saline, will be applied to the superior bulbar conjunctiva of both eyes. Corneal staining type will be graded using the Efron scale (0 to 4, 0.5 steps), staining extent and depth will be graded on a (0 to 4 scale, 1 step) while viewing with cobalt blue light and Wratten filter (if available). Conjunctival staining and indentation will be graded using a 0 to 4 scale (0.5 steps), with larger values indicating increasing severity.

4.5.13 APPLICATION OF PETROLEUM JELLY

Petroleum jelly will be removed from the original container using a cotton tipped applicator and placed in a new paper cup for each participant. Another cotton tipped applicator will be given to each participant to apply thin layer of petroleum jelly to the skin surrounding the eye using a mirror. A new cotton tipped applicator and paper cup will be used for each application. Any remaining petroleum jelly will be disposed of according to UW guidelines.

4.5.14 REMOVAL OF PETROLEUM JELLY

To remove petroleum jelly from the skin, the participant will close their eyes and wipe with a tissue in a nasal to temporal direction, with extra care being paid wiping near the lid margin to avoid contaminating the tear film or contact lenses.

4.5.15 SUBJECTIVE COMFORT RATINGS

Participants will be asked to fill a numerical analog scale for comfort, dryness, and burning or stinging for each eye on a 0-100 scale:

- At Visit 2, before & 15 minutes after lens insertion
- At Visit 3, after at least 6 hours of contact lens wear.

4.5.16 EVAPORIMETRY

The participant will be seated at an adjustable height table and will place their elbows on the table. The participant will hold a pair of modified swimming goggles (Figures 1A and 1B) over their eyes for 20 seconds while their eyes are open. The participant will be prompted to blink every 3 seconds during the measurement using a metronome (<https://www.youtube.com/watch?v=9ypeNJJeKIs>). The goggle will be removed and ventilated in front of a fan until the relative humidity returns to

baseline levels. The goggle will then be placed over the eyes for 20 seconds while they are closed to measure the evaporation rate from the skin. Three consecutive measurements of open eye and closed eye measurements will be taken. Recordings of the temperature and relative humidity during the measurement will be saved as a text file and images of the temperature and humidity versus time plotted as a graph will be saved as a png file. The rate of tear evaporation will be calculated from slope derived from the change in relative humidity over time. The evaporation rate from the ocular surface will be calculated by subtracting the evaporation rate of closed eye from the evaporation rate of the open eye. The average of three ocular surface evaporation rates will be calculated for each eye.

[figure not shown]

Figure 1: (A) Evaporimeter with arrows showing the location of the temperature/humidity sensors in the swimming goggle. (B) View of the front of the evaporimeter.

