2 OBJECTIVES

The objective of the study is to compare the rate of tear evaporation, measured with a novel evaporimeter, before and after DAILIES TOTAL1 and Biotrue ONEday CLs are worn in symptomatic and asymptomatic contact lens wearers.

The primary outcome variable for this study are the slopes calculated from the change in relative humidity over time.

Other variables of interest include:

- Contact lens dry eye questionnaire-8 (CLDEQ-8) score
- Comfort (subjective rating)
- Dryness (subjective rating)
- Non-invasive break up time
- Lipid layer thickness (Tearscope, LipiView II)
- Ocular surface area (mm²)
- Volume inside the goggle (cm³)

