3 HYPOTHESIS

The study hypothesis is that there will be a higher rate of tear evaporation with CL wear compared to when CLs are not worn.

There will also be a significant difference in the rate of tear evaporation of DAILIES TOTAL1 (DT1) and Biotrue ONEday (BOD) after a minimum of 6 hours of CL wear.

There will also be a higher rate of tear evaporation in symptomatic contact lens wearers compared to asymptomatic lens wearers.

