10 STATISTICAL ANALYSIS AND DATA MANAGEMENT

10.1 STATISTICAL ANALYSIS

All data will be analyzed by CORE at the University of Waterloo on unmasked data using Microsoft Excel and statistical analysis software such as GraphPad and SPSS. Interim data analysis will be conducted after 10 symptomatic and 10 asymptomatic participants have completed the study to determine the optimal time period over which to calculate the slope. The results of the interim data analysis will also be used to calculate the sample size.

Descriptive statistics will be provided on information regarding baseline variables (age, sex, contact lens refractive error distribution, etc.). Data may be evaluated for individual groups

(asymptomatic versus symptomatic) and when both groups are combined. Data will be tested for normality of distribution using Shapiro-Wilk tests. A p -value of < 0.05 will be considered statistically significant. Additional analysis may be conducted.

Table 4 lists the primary outcome variables and anticipated statistical procedures.

Table 4: Outcome variables and anticipated statistical procedures

| Variable | Analysis | Statistical test |
|--------------------------------------------------------------------------------------------------------------------------------------------------------------|--------------------------------------------------------------------------------------------------------------------|--------------------------------------------------------------------------------------------------------------------|
| Tear evaporation rate | Change in relative humidity over time | Slope |
| Tear evaporation rate/Time | Effect of lens type | RMANOVA Mauchly's test of sphericity Greenhouse-Geisser p values Tukey HSD post hoc Paired t -test |
| Tear evaporation rate/ Subjective ratings/Non- invasive breakup time/Lp d ayer thickness (Lp View II - continuous)/Area of the ocular surface | Relationship between tear evaporation rate and subjective comfort and dryness/other tear film assessments | Pearson correlation – r |
| Tear evaporation rate/ Lp d ayer thickness (Tearscope - ordinal)/ Volume of the goggle | Relationship between tear evaporation rate and lpdayer thickness | Spearman correlation – ρ |

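### The tear evaporation rate is a relative-humidity slope that ignores the temperature saved beside it; a consistent sensor-air temperature shift would add avoidable bias to the Visit 3 versus no-lens contrast

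*Combined protocol and SAP*

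**What the plan says.** Section 2 sets the outcome: "The primary outcome variable for this study are the slopes calculated from the change in relative humidity over time". Section 4.5.16 repeats this for the tear evaporation rate: "The rate of tear evaporation will be calculated from slope derived from the change in relative humidity over time". Table 4 in section 10.1 gives its analysis as "Change in relative humidity over time", with the slope as the statistical procedure. None of the three contains a temperature term.

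Section 4.5.16 also says: "Recordings of the temperature and relative humidity during the measurement will be saved as a text file". No section then uses the temperature for conversion, as a covariate or as a rule for rejecting a recording. The ocular-surface rate is "calculated by subtracting the evaporation rate of closed eye from the evaporation rate of the open eye". Between readings, "The goggle will be removed and ventilated in front of a fan until the relative humidity returns to" baseline; the end point is a humidity, not a temperature.

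The first hypothesis in section 3 is that "there will be a higher rate of tear evaporation with CL wear compared to when CLs are not worn". All scheduled no-lens evaporimetry is at Visit 2, in the morning (sections 4.1.1 and 4.4.3). The worn-lens reading is at Visit 3, in the afternoon of the same day, after at least 6 hours of wear and with lenses in both eyes (sections 4.1.1 and 4.4.4). No limits on room temperature or humidity are stated; the safeguard given is at least 15 minutes of adaptation to the room.

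The interim analysis after 10 symptomatic and 10 asymptomatic completers is meant "to determine the optimal time period over which to calculate the slope" and to supply the sample size.

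**The concern.** An RH slope is not a pure measure of evaporation. The same mass of vapour entering the goggle raises RH less when the air is warmer, because warmer air needs more vapour to saturate. The outcome therefore mixes vapour flux with the temperature of the air at the sensor.

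This matters most where temperature could line up with the factor being compared. Worn-lens readings after 6 hours always follow the no-lens readings, with no afternoon no-lens reading, no lens-free eye and no randomised order. A temperature shift shared by most participants would enter the Visit 3 versus no-lens difference as if it were an effect of wear. At equal flux, warmer afternoon air works against the first hypothesis and cooler air works in its favour. The data needed to remove this component are already being saved.

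**Working it through.** The plan gives no temperature, variance or power figure on this point, so there is no figure of its own to reproduce. What follows is a sensitivity calculation.

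**Inputs.** From the documents: the outcome is an RH slope with the closed-eye slope subtracted (4.5.16). Assumed: the Magnus saturation formula, sensor air at 24 °C (20 to 30 °C as a range), fixed goggle volume, and identical vapour flux.

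**Scale factor.** Saturation vapour pressure is es(T) = 6.112 × exp[17.62 T/(243.12 + T)] hPa, and saturation vapour density is ρ(T) = 216.68 × es(T)/(T + 273.15) g/m³. Since RH = 100 × vapour density/ρ(T), the RH slope at a given flux is proportional to 1/ρ(T). Moving from T to T + d multiplies it by ρ(T)/ρ(T + d).

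For 24 to 25 °C: ρ(24) = 21.71 and ρ(25) = 22.97, so the ratio is 21.71/22.97 = 0.945, a fall of 5.5%.

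| Shift in sensor air from 24 °C | Change in RH slope, same flux |
|---|---|
| -2 °C | +12.1% |
| -1 °C | +5.9% |
| +0.5 °C | -2.8% |
| +1 °C | -5.5% |
| +2 °C | -10.6% |

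The starting temperature matters little: +1 °C gives -5.66%, -5.49% and -5.25% from 20, 24 and 30 °C.

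**Closed-eye subtraction.** If both slopes carry a factor a, then a × open - a × closed = a × (open - closed). With illustrative slopes of 3 (open) and 1 (closed), the net is 2 at 24 °C. At 25 °C it is 2.835 - 0.945 = 1.890, and 1.890/2 = 0.945. Subtraction can cancel additive warming common to the two recordings, but not the scale factor.

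**Size relative to a lens effect.** A true proportional rise x is exactly offset when (1 + x) × ρ(24)/ρ(24 + d) = 1. For x = 5%, 10% and 20%, d = 0.86, 1.69 and 3.26 °C of sensor-air warming at otherwise equal flux.

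**Effect on a test.** Take no true effect, n = 20, a 5.5% bias (about 1 °C, consistent across participants) and a two-sided 5% paired t-test. The noncentrality is 0.055 × √20/SD, with the SD of the paired difference as a share of the mean rate; at SD = 20% it is 1.23. Rejection rates are 64.6%, 21.5%, 12.2% and 9.0% for assumed SDs of 10%, 20%, 30% and 40%.

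**What conversion would not remove.** Suppose flux is proportional to es(surface) - RH × es(air), with a 34 °C surface and 24 °C air. At 30% RH this is 53.09 - 0.30 × 29.77 = 44.16; at 50% it is 53.09 - 0.50 × 29.77 = 38.21. The fall is 13.5% (10% to 18% over surfaces of 32 to 36 °C and air of 22 to 26 °C). This is a real change in evaporation, so changing the unit leaves it in place.

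**The case against.** The strongest reply is that no drift is shown. The documents give no temperatures and no reason to expect a consistent afternoon shift; a shift that varies in sign between participants is noise, not bias. This stands, and it makes the point conditional.

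Second, the figures concern air at the sensor. The goggle is held against the face for 20 seconds with sensors close to the eye (sections 1 and 4.5.16), so how much of a room change reaches the sensor is unknown. A warmer room might also warm the ocular surface and raise true flux. In the flux model above, at 40% RH and fixed ambient vapour content, an assumed surface rise of 0.1 to 0.5 °C per 1 °C of air shrinks -5.5% to between -4.8% and about -2%. This also stands: the tabulated figures are not room-temperature effects, and on this point they lie towards the upper end.

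Third, the exposed contrast is narrow. Section 1 gives the comparison of the two lenses as the purpose, and both eyes are measured at once. The first hypothesis names no visit, and the time row of Table 4 lists the effect of lens type. Visit 2 compares lens with no lens inside one 1.5-hour visit, though after only about 15 minutes of wear and in fixed order. These limits are right, but section 2 sets a before-and-after-wear objective, and Visit 3 is the only reading after sustained wear.

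Fourth, the traces are saved and section 10.1 allows additional analysis, so conversion could be done later. That is true, but nothing commits to it, and the interim analysis will choose the slope window and sample size on the RH scale.

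**Conclusion.** The point holds as a conditional, inexpensive improvement. As written, the outcome carries a temperature-dependent scale factor of about 5-6% per 1 °C of sensor air at identical flux, which closed-eye subtraction does not remove. If sensor-air temperature shifts consistently between the morning no-lens readings and Visit 3, the result is an avoidable bias in that one contrast. The size of any actual bias is unknown; the drifts and SDs used above are assumptions.

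A reader might infer more than this, and the documents do not support it:

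- That the test of the first hypothesis is already biased. No drift is documented.
- That the comparison of the two lenses is compromised. Simultaneous measurement of both eyes largely protects it.
- That the offsetting drifts of 0.86 to 3.26 °C are room temperatures. They are not.
- That conversion would separate lens wear from time of day. It cannot, because there is no afternoon no-lens reading.
- That absolute humidity must replace RH as the primary scale. Reporting both answers the concern.

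**What to change.** In section 4.5.16 and Table 4, before the interim analysis chooses the slope window and sample size, pre-specify that:

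1. Each RH sample is also converted to absolute humidity in g/m³, (RH/100) × ρ(T), using the same sensor's simultaneous temperature.
2. Open-eye and closed-eye slopes are fitted and subtracted on that scale.
3. The Visit 3 versus no-lens contrast is reported on both the absolute-humidity and RH scales.
4. Starting temperature and RH of each recording are taken from the saved trace and tabulated by visit.
5. The report states that conversion removes the unit scale factor only, and that time of day and ambient humidity remain confounded with wear in this contrast.

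**Cost.** Processing of text files already saved, one table and a short protocol edit, with no added visit or participant procedure. The downside is that temperature-sensor error enters the converted slope. A constant offset of 0.3 °C (assumed) would scale it by ρ(24.3)/ρ(24) - 1 = 1.7%, nearly equally in all conditions: the ratio between a 26 °C and a 24 °C recording would change by less than 0.03%. Sensor lag within a 20-second trace would add error of a size the documents do not allow to be stated, which is one reason to show both scales.

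### The humidity slope is compared between people without adjustment for ocular area or goggle volume, although both are measured; the symptom-group comparison and the correlations are affected, while the lens comparisons are largely protected

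*Combined protocol and SAP*

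**What the plan says.** Section 2 (Objectives) sets the outcome: "The primary outcome variable for this study are the slopes calculated from the change in relative humidity over time". Section 4.5.16 (Evaporimetry) repeats it: "The rate of tear evaporation will be calculated from slope derived from the change in relative humidity over time". Table 4 in section 10.1 has the row "Tear evaporation rate | Change in relative humidity over time | Slope". The stated processing is that the ocular rate "will be calculated by subtracting the evaporation rate of closed eye from the evaporation rate of the open eye", followed by averaging three such differences per eye.

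The two geometric quantities are collected at Visit 1. Section 4.5.10 analyses a photograph of each eye "in order to determine the size of the ocular surface in mm²". Section 4.5.11 fills each side of a matching goggle with saline: "The amount of saline added to each goggle will be recorded in milliliters". In Table 4 they appear only as correlates of the tear evaporation rate: "Area of the ocular surface" in the Pearson row and "Volume of the goggle" in the Spearman row. No section multiplies the slope by volume, divides it by area, or enters either as a covariate. Section 10.1 allows for further analyses but does not specify this one.

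Section 3 (Hypothesis) has three parts: lens wear versus no lens, DT1 versus BOD, and symptomatic versus asymptomatic wearers. Only the third compares different people.

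**The concern.** A humidity slope is not evaporation per unit of eye surface. The same tear film should give a steeper slope behind a goggle that traps less air, or in an eye with a wider exposed surface. Subtracting the closed-eye slope does not remove this. Both slopes are divided by the same air volume, and the remaining ocular term still scales with exposed area.

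Three uses of the outcome are affected:

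- In the symptom-group comparison, differences in face and lid shape enter as noise, or as bias if the groups differ in mean area/volume.
- The correlations of the rate with comfort, dryness, break-up time and lipid thickness are pulled towards zero.
- The correlations with area and volume can appear even if neither is related to evaporation per unit area. Table 4 does not say how they are to be read, so a significant result could be taken for physiology.

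The interim data are also to supply the final sample size. If that calculation rests on the symptom-group comparison, which the documents do not say, the inflated variance carries into it.

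**Working it through.** **Nothing to reproduce.** Section 4.2.1 says that no sample size calculation was done, and no SD or CV is given for the slope, area or volume. From the documents come the target of at least 10 completers per group, the ceiling of 50 participants (25 per group if equal) and the 0.05 threshold. All CVs below are assumptions, as are the two-sided test, the 80% power and the group ratio of 1.30.

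**Model.** For a sealed, well-mixed chamber and an early, near-linear rise, slope = k × E × A / V. Here E is evaporation per unit area, A ocular area, V trapped air volume, and k depends on temperature. On the log scale: log slope = log E + log A − log V + constant.

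**Formulas.** For a log-normal quantity, s² = ln(1 + CV²). With E, A and V independent:

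- variance ratio, slope to E: (sE² + sA² + sV²) / sE²
- a true correlation of 0.50 with log E is seen as 0.50 / √(variance ratio)
- n per group (normal approximation) = 2 × (1.96 + 0.8416)² × s² / (ln 1.30)²

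**Inputs.** CV 30% gives s² = 0.0862. CVs of 5%, 10%, 15% and 20% give 0.0025, 0.00995, 0.02225 and 0.0392.

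**Example, 20% each.** Total = 0.0862 + 2 × 0.0392 = 0.1646, and 0.1646 / 0.0862 = 1.91. A correlation of 0.50 becomes 0.50 / √1.91 = 0.36. With 2 × 2.8016² = 15.70 and (ln 1.30)² = 0.0688, n = 15.70 × 0.1646 / 0.0688, which rounds up to 38. With anatomy removed without error, n = 15.70 × 0.0862 / 0.0688, which rounds up to 20.

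| CV of area and of volume, each | Variance ratio | Correlation of 0.50 seen as | n per group | Power, 10 per group | Power, 25 per group |
|---|---|---|---|---|---|
| 0 (anatomy removed) | 1.00 | 0.50 | 20 | 0.52 | 0.88 |
| 5% | 1.06 | 0.49 | 21 | 0.49 | 0.87 |
| 10% | 1.23 | 0.45 | 25 | 0.44 | 0.81 |
| 15% | 1.52 | 0.41 | 30 | 0.37 | 0.73 |
| 20% | 1.91 | 0.36 | 38 | 0.30 | 0.63 |

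Over the same rows the ratio runs from 1.13 to 3.00 if the CV of E is 20%, and from 1.03 to 1.53 if it is 40%.

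**Area and volume correlated.** The total becomes sE² + sA² + sV² − 2ρ·sA·sV. With equal CVs and an assumed ρ of 0.5, the last three terms reduce to a single s². At 20% each the ratio is (0.0862 + 0.0392) / 0.0862 = 1.46 instead of 1.91. At 10% it is (0.0862 + 0.00995) / 0.0862 = 1.12 instead of 1.23.

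**Correlations created by geometry.** Simulation used E unrelated to A and V, a CV of E of 30%, one value per person and 4,000 runs per setting. Chance of p < 0.05, nominal 5%:

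| CV each | Area (Pearson), n = 20 | Area, n = 50 | Volume (Spearman), n = 20 | Volume, n = 50 |
|---|---|---|---|---|
| 5% | 11% | 22% | 10% | 18% |
| 10% | 26% | 58% | 23% | 54% |
| 15% | 42% | 83% | 39% | 82% |
| 20% | 59% | 93% | 57% | 94% |

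The mean correlation with area runs from 0.16 to 0.47, and with volume from −0.15 to −0.46. With anatomy divided out without error, both tests return to about 5%.

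**Possible bias.** Suppose E is equal in the two groups but mean A/V differs by 10%, with CVs of 30%, 10% and 10%. The group test then rejects in that direction in about 10% of trials at 10 per group and 18% at 25 per group, against a nominal 2.5%.

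**Within-person comparisons.** In one eye over time, a constant A/V cancels from the ratio: a 20% rise in E gives 1.20 whatever A/V is. Only the absolute difference is rescaled, to 0.2 × 0.7 = 0.14, 0.20, or 0.2 × 1.3 = 0.26 for A/V factors of 0.7, 1.0 and 1.3. Between fellow eyes, left-right differences in A/V remain as noise.

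**The case against.** The strongest reply has four parts.

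**The main comparisons are within person.** The objective concerns change with lens wear, and DT1 and BOD are randomised to fellow eyes. A stable area/volume ratio cannot create a lens-wear effect in the same eye, and randomisation prevents systematic left-right bias. This stands. A reader might infer that anatomy undermines the primary outcome throughout; the documents do not support that.

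**The scaling law is an assumption.** The goggle is hand-held for 20 seconds, the sensors sit close to the eye, and the slope window is left to the interim analysis. Whether total volume governs the slope in this prototype is an empirical matter. This stands for the exact form. The direction is hard to dispute, and the Introduction itself presents less surplus air as an advantage.

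**Slope × volume / area may be no better than the raw slope.** Volume is measured once, strapped and with eyes closed, while the ocular reading is hand-held with eyes open. Area comes from a Visit 1 photograph listed before the study lenses are removed. With a CV of E of 30%, a 10% error in each quantity inflates the log variance of the normalised rate by (0.0862 + 2 × 0.00995) / 0.0862 = 1.23, exactly what uncorrected 10% anatomical CVs would do. The formula also leaves out temperature, which is recorded but not used to convert relative humidity to water mass. This stands. The tempting step of making the normalised rate the main outcome is therefore not supported.

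**The area and volume correlations may be meant as device checks.** The study also aims to validate the evaporimeter, so they are legitimate in that role. This stands, but Table 4 does not say so.

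**Conclusion.** The concern holds for the between-person analyses. The symptom-group comparison and the correlations with comfort, dryness, break-up time and lipid thickness use a slope that should carry anatomy the trial measures and does not adjust for. The area and volume correlations are partly geometric; a genuine biological link is not excluded.

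The size cannot be derived from the documents. Under the assumed 30% CV for evaporation per unit area and independent CVs of 5% to 20% each for area and volume, between-person slope variance is inflated about 1.06 to 1.9 times. At the low end this is negligible (21 against 20 per group); at the high end it is not (38 against 20). Positive correlation between area and volume shrinks it. Bias needs a group difference in area/volume, for which the documents give no evidence either way. All of this rests on an approximately sealed, well-mixed goggle.

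The documents do not support concluding that the lens-wear or DT1 versus BOD results would be invalid. There, anatomy mainly rescales absolute differences and adds some noise.

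**What to change.** In section 10.1 and Table 4:

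1. Keep the slope (open minus closed) as the primary outcome.
2. For the symptom-group comparison, analyse log slope, or slope, with log ocular area and log goggle volume as covariates. Choose the scale in advance; the log needs positive net slopes. Table 4 names no test for this comparison, so the model can be written in at the same time.
3. Give the between-person correlations with comfort, dryness, break-up time and lipid thickness the same adjustment, as partial correlations.
4. Pre-specify (open minus closed slope) × volume / area, per eye, as a sensitivity analysis.
5. Label the area and volume correlations as a check of the device and its geometry.

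The cost is wording and a few lines of analysis, with no new measurement. The adjustment uses about two degrees of freedom: with 20 participants in two groups, residual degrees of freedom fall from 18 to 16. Measurement error in area and volume makes the adjustment incomplete, and in the normalised rate it multiplies directly into the result. That is why the normalised rate should stand beside the slope and not replace it.
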